**16.6 Inclusion of Women and Minorities**

16.61 This study will be available to all eligible patients, regardless of race, gender, or ethnic origin.

16.62 There is no information currently available regarding differential effects of this regimen in subsets defined by race, gender, or ethnicity, and there is no reason to expect such differences to exist. Therefore, although the planned analysis will, as always, look for differences in treatment effect based on racial and gender groupings, the sample size is not increased in order to provide additional power for subset analyses.

16.63 The geographical region served by MCCC has a population which includes approximately 3% minorities. Based on prior MCCC studies involving similar disease sites, we expect about 3-5% of patients will be classified as minorities by

race and about 100% of patients will be women. Expected sizes of racial by gender subsets are shown in the following table:

16.64 Table of Accrual by Ethnicity/Race/Gender

Accrual Targets			
Ethnic Category	Sex/Gender		
	Females	Males	Total
Hispanic or Latino	1	0	1
Not Hispanic or Latino	37	0	37
Ethnic Category: Total of all subjects	38	0	38
Racial Category			
American Indian or Alaskan Native	0	0	0
Asian	1	0	1
Black or African American	1	0	1
Native Hawaiian or other Pacific Islander	0	0	0
White	36	0	36
Racial Category: Total of all subjects	38	0	38

**Ethnic Categories:**

**Hispanic or Latino** – a person of Cuban, Mexican, Puerto Rican, South or Central American, or other Spanish culture or origin, regardless of race. The term “Spanish origin” can also be used in addition to “Hispanic or Latino.”

**Not Hispanic or Latino**

**Racial Categories:**

**American Indian or Alaskan Native** – a person having origins in any of the original peoples of North, Central, or South America, and who maintains tribal affiliations or community attachment.

**Asian** – a person having origins in any of the original peoples of the Far East, Southeast Asia, or the Indian subcontinent including, for example, Cambodia, China, India, Japan, Korea, Malaysia, Pakistan, the Philippine Islands, Thailand, and Vietnam. (Note: Individuals from the Philippine Islands have been recorded as Pacific Islanders in previous data collection strategies.)

**Black or African American** – a person having origins in any of the black racial groups of Africa. Terms such as “Haitian” or “Negro” can be used in addition to “Black or African American.”

**Native Hawaiian or other Pacific Islander** – a person having origins in any of the original peoples of Hawaii, Guam, Samoa, or other Pacific Islands.

**White** – a person having origins in any of the original peoples of Europe, the Middle East, or North Africa.

## 17.0 Pathology Considerations/Tissue Biospecimens

### 17.1 Summary Table of Research Tissue Specimens to be Collected for this Protocol

Correlative Study (Section for more information)	Type of Tissue to Collect	Block, Slides, Core, etc. (# of each to submit)	Baseline	End of Cycle 1 (prior to pembro)	End of Tx for any reason	Process at site? (Yes or No)	Temperature Conditions for Storage /Shipping
Tumor infiltrating lymphocytes (Section 17.41)	FFPE	H&E slide and 5 unstained slides of 5 microns.	Mandatory	Optional	Optional	Yes	Ambient
Immunohistochemistry for PD-L1 (Section 17.42)	FFPE	2 unstained slides of 5 microns	Mandatory	Optional	Optional	Yes	Ambient
Gene expression analysis (Section 17.43)	FFPE	10 unstained slides of 5 microns	Mandatory	Optional	Optional	Yes	Ambient
PDJ amplification (Section 17.44)	FFPE	2 unstained slides of 5 microns	Mandatory	Optional	Optional	Yes	Ambient

NOTE: First biopsy\* is mandatory, second and third are optional. (\*Unless adequate tissue is available from biopsy obtained  $\leq$ 90 days prior to registration)

NOTE: Tests are listed in order of priority. If insufficient material to do all items, start with top and work down.

**17.2** Diagnostic Slides from Original and /or Recurrent Tissue

Please see the number of required unstained slides for each test in the table. Slides should be sent to BAP lab in Jacksonville

Along with original diagnostic slides, include pathology reporting form, surgical pathology report and operative report.

**17.3** Correlative Tissue Collection

17.31 Tissue Kits will not be provided for this protocol. Kits will be supplied by the Mayo Florida Biospecimen Acessioning and Processing Shared Resource (BAP). See section 14.31 on how to order kits.

[figure not shown]
**17.32** Paraffin Embedded Tissue

17.321 Submit H&E as well as uncharged, unstained slides – see table. Do not use coverslips, do not bake. 5 micron thick sections on uncharged slides at ambient temperature.

17.322

17.33 Correlative Tissue will be sent to:

**17.4** Background and Methodology**17.41** Tumor infiltrating lymphocytes

Given that tumor infiltrating lymphocytes (TILs) have been shown to correlate with patients' outcome in several tumor types, we plan to evaluate both stromal and intraepithelial TILs in patient samples from this trial. Besides H&E, more comprehensive evaluation of TILs will be performed using immunohistochemistry (IHC) staining for CD4, CD8, CD25, and FOXP3 as we previously published {Knutson 2015}.

**17.42** Immunohistochemistry for PD-L1

Since PD-L1 expression had been shown to correlate with response to anti-PD1 therapy in the past, we also plan to evaluate PD-L1 expression by immunohistochemistry {Topalian 2012}

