### 1.6 Correlative studies

Currently, there are several correlative studies that are being investigated as biomarkers for immunotherapy in cancer. Immune checkpoint blockade agents, like pembrolizumab, exerts its activity by blocking the distinct immunosuppressive checkpoints PD-1 or its major ligand PD-L1. Previous studies demonstrated that PD-L1 expression in the tumors appears to correlate with improved outcome in patients treated with immune checkpoint blockade agents {Topalian, 2012}. Furthermore, studies also showed that immune checkpoint blockade agent can also increase tumor infiltrating lymphocytes and improve response to adoptive cell therapy (1).

As described in the previous rationale section, MEK inhibition has been shown to upregulate cell surface MHC expression as well as PD-L1 in both *in vivo* and *in vitro* triple negative breast cancer models. Moreover, the combination of MEK and immune checkpoint blockade agent were synergistic and enhanced antitumor immune responses were observed *in vivo* breast cancer syngeneic mouse models {Balko 2014}. Nevertheless, the effects of MEK inhibitors to immune response in human remain largely unknown.

To evaluate immunologic response to single agent binimetinib and the combination of binimetinib and pembrolizumab, several correlative studies will be carried out as followed:

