**3.2 Registration – Exclusion Criteria**

3.21 Any of the following because this study involves an investigational agent whose genotoxic, mutagenic and teratogenic effects on the developing fetus and newborn are unknown:

- Pregnant women
- Nursing women
- Men or women of childbearing potential who are unwilling to employ adequate contraception as defined in [Section 9.0](#).

3.22 Receiving any other investigational agent which would be considered as a treatment for the primary neoplasm  
OR  
Participated in a study of an investigational agent, received study therapy or used an investigational device  $\leq 4$  weeks prior to registration

3.24 Immunocompromised patients and patients with known immunodeficiency; or receiving systemic steroid therapy or any other immunosuppressive therapy  $\leq 7$  days prior to registration.

NOTE: Inhaled steroids and low-dose corticosteroids are allowed (see [Section 9.0](#)).

3.25 History of active tuberculosis (TB), human immunodeficiency virus (HIV), active hepatitis B (e.g., HBsAg reactive) and/or active hepatitis C infection (e.g. HCV RNA qualitative is detected).

3.26 Received a live vaccine  $\leq$ 30 days prior to registration.  
NOTE: Seasonal influenza vaccines for injection are generally inactivated flu vaccines and are allowed; however intranasal influenza vaccines (e.g., Flu-Mist®) are live attenuated vaccines, and are not allowed.

3.27 Hypersensitivity to pembrolizumab, binimetinib, or any excipients of either drug.

3.28 Prior anti-cancer therapy with a monoclonal antibody (mAb)  $\leq$ 4 weeks prior to registration  
OR Failure to recover (to  $\leq$ Grade1) from adverse events (AE) attributable to agents received  $>$ 4 weeks prior to registration.

3.29a Prior therapy including chemotherapy, targeted small molecule therapy or radiation therapy  $\leq$ 2 weeks prior to registration  
OR Failure to recover (to  $\leq$ Grade1 or to baseline) from adverse events (AE) attributable to agents received  $>$ 4 weeks prior to registration.  
NOTE: Exception for neuropathy  $\leq$ Grade 2, which is allowed.

3.29b Any active central nervous system (CNS) lesion (i.e., those with radiographically unstable, symptomatic lesions) and/or leptomeningeal metastases.  
NOTE: Patients treated with stereotactic radiotherapy or surgery are eligible if no evidence of CNS disease progression  $\geq$ 4 weeks and patients must be off corticosteroid therapy for  $\geq$ 3 weeks.  

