- For Vascular abnormalities: fluorescein angiography of central 30 degrees.

 Whole blood samples for correlative research will be collected at the following timepoints: Baseline, 2nd week of binimetinib prior to starting pembrolizumab, After 1 cycle of bini and pembro at Cycle 3, Cycle 9, Day 1 (only if  $>6$  months of stable disease/CR/PR), and at the end of therapy (i.e.,  $\leq 4$  weeks after final administered dose of therapy), or at the time of tumor recurrence.

 Submission of tissue from the primary or metastatic tumor is mandatory

 Mandatory tumor biopsy except in patients who have adequate tumor tissue samples collected  $\leq 90$  days prior to registration. Adequate sample is defined as core needle, punch, or incisional biopsy samples that can provide  $\geq 10$  unstained sections of 5  $\mu$ M thickness. Fine needle aspiration (FNA) sample alone is not sufficient.

 An optional newly-obtained core or excisional biopsy (FNA not adequate) is requested after 10 days of binimetinib prior to starting pembrolizumab and at the end of treatment for any reason.

 Physical exam includes gross perimeter test. After baseline, patients receiving binimetinib should be assessed at every physical examination for decreased

Tests and procedures			Active Treatment								End of Treatment	Post-Treatment
	$\leq 28$ days prior to registration	$\leq 14$ days prior to registration	Pre-Tx biopsy	Cycle 1 binimeti nib alone	Cycles 2-3 with pembro		Cycles 4-8	Cycle 9	Cycle 10 and beyond	At time of disease progression	Safety follow up: 30 days post- discontinuation	
Window					$\pm 3$ days	$\pm 3$ days	$\pm 3$ days	$\pm 3$ days				
Patient Medication Diary (See Appendix II)				X		X	X	X	X	X		

---

visual acuity using a gross perimetry test (as opposed to automated visual field testing). Symptomatic patients should be referred for a full ophthalmic consultation.

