#### 7.13 Treatment Plan

All trial treatments will be administered on an outpatient basis.

In Cycle 1, patients will receive binimetonib for 2 weeks followed by blood draw and optional tumor biopsy to evaluate the effects of binimetonib single agent on immune system and tumors prior to starting pembrolizumab in Cycle 2 and every subsequent cycle.

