### 16.3 Statistical Analysis Plan

The objective of the phase I portion of the study is to estimate the maximum tolerated dose (MTD) using the standard 3+3 design. Safety/adverse events data will be tabulated, including adverse events of all grades.

For the phase II portion of the study, the overall response rate by RECIST will be estimated using the approach of Jung and Kim [On the estimation of the binomial probability in multistage clinical trials. Stat Med 23:881-96, 2004]. The 90% lower confidence bound will be calculated using the approach of Koyama and Chen [Proper inference from Simon's two-stage designs. Stat Med 27:3145-54, 2008]. Secondary efficacy endpoints include objective response rate by immune-related response criteria (irRECIST), progression-free survival (PFS) and overall survival (OS). Objective response rate by irRECIST will be estimated as a binomial proportion with a 2-sided 95% CI. PFS will be defined as the time from study enrollment to date of progression. Patients who have not progressed (including those lost to follow-up) at the time of data analysis will be censored at the date last known to be free of progression. OS will be defined as the time from study enrollment to death attributable to any cause (i.e. death from breast cancer, non-breast cancer cause, or from unknown cause). Patients who are alive (including those lost to follow-up) at the time of data analysis will be censored at the last known alive date. A Kaplan-Meier curve will be used to summarize the PFS and OS experience of this patient cohort.

Baseline TILs and percent change in TILs from baseline will be summarized. Logistic regression models will be used to assess the correlation between these biomarkers and ORR in order to assess their prognostic significance. Cox Proportional Hazard models will be used to assess their correlation with time-to-event endpoints such as PFS and OS. Similar analyses will be performed for other exploratory biomarkers such as immune related gene signature, PDJ amplification, etc. These analyses will be exploratory in nature. As such, no adjustment for multiple comparisons will be made; all hypothesis tests will be based on 2-sided alpha = 0.05 level.

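### Tissue up to 90 days old can serve as baseline even if other therapy followed it, so in those patients the tissue change over Cycle 1 cannot be ascribed to single-agent binimetinib

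*Combined protocol and SAP*

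**What the plan says.** Footnote 10 of the study calendar (Section 4.1) reads "Mandatory tumor biopsy except in patients who have adequate tumor tissue samples collected" no more than 90 days before registration, and the note under the table in Section 17.1 repeats the waiver: the first biopsy is mandatory "Unless adequate tissue is available from biopsy obtained" within the same 90 days. The test of adequacy is technical: "Adequate sample is defined as core needle, punch, or incisional biopsy samples that can provide" at least 10 unstained sections, with fine needle aspirates alone ruled out. On source, footnote 9 says "Submission of tissue from the primary or metastatic tumor is mandatory".

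The exclusion criteria limit how recent earlier treatment may be. Under 3.29a, "Prior therapy including chemotherapy, targeted small molecule therapy or radiation therapy" excludes a patient if given within 2 weeks of registration. Under 3.28 the limit for monoclonal antibodies is 4 weeks. Prior lines are unlimited in phase I and capped at three metastatic lines in phase II (3.15).

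Section 7.13 gives the purpose of the two-week run-in: the blood draw and optional biopsy are there "to evaluate the effects of binimetonib single agent on immune system and tumors prior to starting pembrolizumab". Section 16.3 states "Baseline TILs and percent change in TILs from baseline will be summarized", relates these measures to ORR, PFS and OS (goals 2.31 and 2.32), and plans similar analyses for the gene signature. It makes no provision for intervening therapy, specimen age or specimen site.

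**The concern.** A change score isolates a drug effect only if nothing else happened between the two specimens. Here a patient can be biopsied at one progression, receive a further line of therapy, complete the washout, register, and still have the older specimen count as baseline. The difference to the end-of-Cycle-1 biopsy then contains the effect of that line as well as that of binimetinib.

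The protocol's own background gives reason to expect therapy to move the marker. Section 1.5 cites a trend to lower TILs in patients without a pathologic complete response to neoadjuvant chemotherapy (p = 0.07), and Section 1.6 says that "immune checkpoint blockade agent can also increase tumor infiltrating lymphocytes". At stake is the tissue half of what the run-in was built to show. The associations of change with outcome are at stake to a lesser degree.

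**Working it through.** The plan states no power or precision for the tissue correlatives, so there is no figure of its own to reproduce. The check is day arithmetic on the stated windows, followed by two illustrations on assumed values.

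**1. Room for intervening therapy.** Count back from registration (day 0).
- Oldest admissible tissue: day -90.
- Chemotherapy, small molecules and radiation: excluded within 14 days, so the last permitted dose is on day -15. Span: 90 - 15 = **75 days**. On a three-weekly schedule this holds doses at 0, 21, 42 and 63 days after the biopsy, four in all.
- Monoclonal antibodies: excluded within 28 days, so the last permitted dose is on day -29. Span: 90 - 29 = **61 days**, or three doses (0, 21 and 42 days).

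**2. Age of the baseline specimen.** Treatment starts no more than 14 days after registration (Section 6.34).
- At first binimetinib dose: 90 + 14 = 104 days.
- At a biopsy after 10 days of binimetinib: 104 + 10 = 114 days.
- At the end of Cycle 1: 104 + 14 = **118 days**, against 10 to 14 days of binimetinib.

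**3. Error in the mean change.** Let f be the share of pairs with intervening therapy and d the shift in TILs, in points, which that therapy caused. On the absolute scale:

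observed mean change = binimetinib effect + f × d

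The documents give neither f nor d. For assumed d between -10 and +10 points, the error is at most 0.25 × 10 = 2.5 points at f = 0.25, 5 points at f = 0.5 and 10 points at f = 1, in either direction. Section 16.3 uses percent change, where the older value is also the denominator, so the error there depends on the baseline level too.

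**4. Associations with response, as illustration only.** Assume 23 pairs, 30-50% of them with intervening therapy, a shift of 1 to 1.5 SD with an extra SD of 1, and a two-group comparison of change by response at the 5% level. Across separate simulation runs with a true effect of about 1.05 to 1.1 SD:
- Power with no contamination is about 60-64%. With contamination and all pairs it is 31-49%.
- If there is no true association but affected patients respond less often (10% against 45%, assumed), the test rejects in 6.5-15% of runs.
- With clean pairs only, rejection under the null is 4-6% and power is 31-46%.

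**5. Which analyses are exposed.** Only patients with all three features: archival tissue, therapy after it, and consent to a later optional biopsy. The confounding with binimetinib alone concerns the end-of-Cycle-1 pair, because an end-of-treatment pair normally reflects both drugs. Research blood has its own prospective baseline draw (Section 14.1), so goals 2.33 to 2.35 are unaffected. So are the phase I MTD and the phase II ORR.

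**The case against.** The strongest reply is that little follows for this trial. Section 16.3 labels the analyses exploratory, with no multiplicity adjustment, and no decision depends on them. That stands, and it limits the weight of the point. It does not remove it: exploratory status excuses unadjusted testing, but not a baseline that precedes another treatment.

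Second, 23 pairs is the whole maximum evaluable phase II cohort, while both later biopsies are optional. The affected share, the shift and the response rates in the illustration have no source in the documents. This stands. With 12 pairs and the same 30-50% affected, null rejection is only about 5-7%, and restricting to clean pairs lowers power from roughly 19-25% to 11-21%. At 23 pairs with 10% affected, null rejection is 5-6%. A reader might infer that the outcome associations will be seriously biased, or that affected pairs must be dropped from them. The documents support neither. Nor do they say that patients treated within the 90 days have a worse prognosis.

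Third, a reader might infer that tissue from another lesion also mixes in a therapy effect. It does not: it adds lesion-to-lesion variation. It is also not peculiar to archival tissue, since fresh biopsies have no same-lesion rule either.

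Fourth, the data may already be held. Section 17.2 asks for pathology and operative reports, and the case report form packet is not part of the documents. That makes the repair cheap, but Section 16.3 still does not call for the data to be used. The one prior-treatment factor listed (12.1) is a count, which cannot identify affected pairs.

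**Conclusion.** The point holds as a defined gap in an exploratory analysis. Followed as written, the rules allow up to 75 days of other treatment (61 for an antibody) inside a change meant to show 10 to 14 days of binimetinib. In a patient to whom this applies, the end-of-Cycle-1 change in TILs or gene signature cannot be ascribed to binimetinib alone. The gap is one of omission: the documents do not expressly invite intervening therapy, but no rule prevents it and the washouts are compatible with it.

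The day counts rest on the protocol's windows alone. How many patients are affected, and by how much, cannot be derived from the documents. The power and error figures hold only under the assumed 23 pairs with 30-50% affected, and should not be read as a forecast. The associations with ORR, PFS and OS may be diluted or biased, but the documents do not show that they will be.

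**What to change.** Amend Sections 16.3 and 17.1 as follows.

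- Record for each tissue specimen its date, set against the last dose of prior anticancer therapy, and its site (primary or which metastatic organ).
- Flag any pair in which anticancer therapy was given after the baseline specimen and before the first dose of binimetinib.
- Base any statement about the effect of single-agent binimetinib on tissue on unflagged end-of-Cycle-1 pairs.
- For goals 2.31 and 2.32, report the associations of change with ORR, PFS and OS in all pairs, together with a sensitivity analysis limited to unflagged pairs. Give the number of pairs in each.
- Keep flagged patients in the analyses of baseline values.
- Separately, and descriptively, tabulate same-site and different-site pairs.

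The cost is two data fields, one further analysis and fewer pairs in the restricted set. Date and site should be obtainable from the pathology report named in Section 17.2, and the last prior dose must be known already to check 3.28 and 3.29a. No extra biopsy is needed and the sample size does not change. Using the restriction as a sensitivity analysis for the associations, not as an exclusion, avoids losing power when pairs are few.

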17.43 Gene expression analysis

Global assessment of immune-related gene expression in pre- and post-treatment tumors will be assessed to potentially identify baseline gene expression signature and/or changes in gene expression that may predict response to this combination.

Gene expression analysis will be performed using NanoString platform with the nCounter GX Human ImmunologyV2 panel comprised of 594 immune-related and 15 reference genes.

17.44 PDJ amplification

We have recently reported that approximately 30% of patients with TNBC harbor PDJ amplification {Barrett 2015}. Locating at chromosome 9p24.1, this amplicon encompasses JAK2, PD-L1, and PD-L2 genes. TNBC patients with PDJ amplification had worse disease free (25.0% vs. 66.0%, p = 0.005) and overall survival (25.0% vs. 69.0%, p = 0.004). This amplicon has been previously described in the majority of Hodgkin's lymphoma, which has been reported to have remarkable response to nivolumab (86% clinical benefit rate in heavily pretreated patients) {Ansell 2015}. Based on these intriguing results, we plan to correlate PDJ amplification and clinical outcome of patients in this trial.

